### 8.6.3 Physical and neurological examination

Summaries of shift from Baseline to Visit 9/ET will be provided based on categories normal, abnormal, not clinically significant, and abnormal, clinically significant for each of the single neurological examinations. Summaries of shift from Baseline normal to any post-baseline abnormal, clinically significant category for each of the neurological examinations will also be provided. For physical examination, summaries of shift from Baseline normal to any post-baseline abnormal, clinically significant category will be presented.

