11.7.5 Physical examination

The physical examination should be performed by a medically qualified clinician licensed to perform the examination, according to the tabular schedule of study procedures in Section 5.2. If possible, the same clinician should conduct all physical examinations for the same subject during the study. Subsequent to Visit 1, clinically significant physical examination findings should be reported as AEs.

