11.7.6 Neurological examination

Neurological examinations will be performed by a medically qualified clinician with documented training in the conduct of neurological examinations, according to the tabular schedule of study procedures in Section 5.2. If possible, the same clinician should conduct all neurological examinations for the same subject during the study. The investigator or subinvestigator is responsible for confirming the diagnosis of generalized seizures.

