13.3.3 Other safety analyses

Other variables assessing safety are: ECG, measurements of laboratory parameters (hematology, clinical chemistry, urinalysis, and hormone status) and vital signs (including body weight, height and BMI), physical and neurological examination findings, assessments of Tanner stage (if applicable), Achenbach CBCL, and BRIEF-P/BRIEF.

Measurement and change from Baseline in continuous parameters (eg, vital signs and laboratory measurements) will be summarized using descriptive statistics. When analyzing

categorical data (eg, overall assessment of 12-lead ECG) the number and percentage of subjects in each category will be presented. In addition, shift tables may be used to evaluate the number and percentage of subjects having a different post-Baseline status when compared to their Baseline status.

The analysis of the Bayley-III scales data will be performed in the follow-up study, SP848.

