### **3 DATA ANALYSIS CONSIDERATIONS**

#### **3.1 General presentation of summaries and analyses**

Statistical analysis and generation of tables, figures, subject data listings, and statistical output will be performed using SAS Version 9.4 or higher. All tables and listings will use Courier New font size 9.

Descriptive statistics will be displayed to provide an overview of the study results. If not stated otherwise, all summaries will be displayed overall and by age group ( $\geq 1$  month to <4 years,  $\geq 4$  to <12 years, and  $\geq 12$  to <18 years). For categorical parameters, the number and percentage of subjects in each category will be presented. If not stated otherwise, the denominator for percentages will be based on the number of subjects in the respective population. Unless otherwise noted, all percentages will be displayed to 1 decimal place. No percentage will be displayed for zero counts, and no decimal will be presented when the percentage is 100%. For continuous parameters, descriptive statistics will include number of subjects (n), mean, standard deviation (SD), median, minimum, and maximum.

Decimal places for descriptive statistics will always apply the following rules:

- “n” will be an integer.
- Mean, SD, and median will use 1 additional decimal place compared to the original data.
- Coefficient of variance (CV[%]) will be presented with 1 decimal place.
- Minimum and maximum will have the same number of decimal places as the original value.

A complete set of data listings containing all documented data and all calculated data (eg, change from Baseline) will be generated, and will be sorted by site, subject number and visit (where applicable).

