**Table 8–2: Electrocardiogram Abnormality Criteria**

Parameter	Age Range	Abnormality Criteria
	6m-<3y	<90, >130
	3y-<12y	<60, >130
	>12y	<50, >120

bpm=beats per minute; m=months; ms=milliseconds; QTc=corrected QT interval; y=years.  
A month is defined as 30 days; a year is defined as 365.25 days.

Treatment-emergent ECG abnormalities are defined as values meeting the criteria given in Table 8–2 at any post-Baseline visit during the Treatment Period (including unscheduled visits) and not meeting the same criteria during Baseline.

For ECGs, baseline will be defined as the average of all pre-dose interpretable readings. For all post-baseline visits, the average of all interpretable readings at the specified visit will be used for summaries.

Observed results and changes from Baseline in ECG results will be summarized for all visits and the Last Visit.

The number and percentage of subjects with no abnormality, an abnormal but not clinically significant finding, and a clinically significant finding, will be summarized by visit, including last visit. Percentages will be relative to the number of subjects with an ECG assessment at the respective visit. Subjects are counted once at each visit based on the worst observed outcome across all abnormalities reported at that visit.

Summaries of shifts from Baseline to post-Baseline visits (including Last Visit) will also be provided based on the categories normal, abnormal, not clinically significant, and abnormal, clinically significant.

The number and percentage of subjects with treatment-emergent ECG abnormalities will be presented by visit and treatment group. Abnormalities reported at an unscheduled visit will be summarized under the scheduled visit preceding the unscheduled visit (if the abnormality was not present already at the preceding scheduled visit). Percentages will be based on the number of nonmissing values for the variable and visit. In addition, a listing including all ECG parameter values for subjects meeting any abnormality criteria will be provided.

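### Both any-visit examination tables in SAP 8.6.3 count only children with a normal Baseline, so worsening from a not clinically significant Baseline abnormality is undercounted there (minor)

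*SAP*

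**What the plan says.** SAP 8.6.3 plans three examination summaries.

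1. Neurological, fixed visit, all three categories: "Summaries of shift from Baseline to Visit 9/ET will be provided based on categories normal, abnormal, not clinically significant, and abnormal, clinically significant".
2. Neurological, any visit: "Summaries of shift from Baseline normal to any post-baseline abnormal, clinically significant category for each of the neurological examinations will also be provided".
3. Physical, any visit: "For physical examination, summaries of shift from Baseline normal to any post-baseline abnormal, clinically significant category will be presented". No other physical examination table is planned.

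Section 8.6.3 states no denominator, so the default in SAP 3.1 (subjects in the respective population) would apply.

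Other parts of the documents treat Baseline status differently. For ECGs, which use the same three categories, the SAP says: "Summaries of shifts from Baseline to post-Baseline visits (including Last Visit) will also be provided based on the categories normal", with no filter on a normal Baseline. Protocol 13.3.3 says that "shift tables may be used to evaluate the number and percentage of subjects having a different post-Baseline status when compared to their Baseline status".

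On adverse events, Protocol 11.7.5 says of the physical examination: "Subsequent to Visit 1, clinically significant physical examination findings should be reported as AEs". Protocol 11.7.6, on the neurological examination, has no such sentence. SAP 3.1 adds: "A complete set of data listings containing all documented data and all calculated data (eg, change from Baseline) will be generated".

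**The concern.** For a child who was not CS at Baseline there are two routes to a new CS finding: from normal and from NCS. Both are on-treatment worsening, and an any-visit table is the natural place to show either. Tables 2 and 3 admit only the first route, so any error goes one way, towards fewer events.

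The population makes the second route plausible. SAP 4.8 plans subgroups for West, Lennox-Gastaut and Dravet syndromes and other symptomatic generalized epilepsy. Protocol 7.2 allows dosing by feeding tube, and Protocol 11.7.4 limits orthostatic measurements to ambulatory subjects. That Baseline abnormalities will be common is an inference from these provisions; neither document gives a rate.

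At stake is how completely the examination tables describe worsening in a study whose first-listed objective is safety and tolerability.

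**Working it through.** The plan states no figure to reproduce: the tables are descriptive and the 50 subjects were set without a formal calculation. The check is to follow each transition into CS through the three tables.

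| Baseline → later finding | Table 1 (neuro, Visit 9/ET) | Table 2 (neuro, any visit) | Table 3 (physical, any visit) |
|---|---|---|---|
| Neuro, normal → CS at any visit | if present at Visit 9/ET | yes | – |
| Neuro, NCS → CS, present at Visit 9/ET | yes | no | – |
| Neuro, NCS → CS elsewhere, absent at Visit 9/ET | no | no | – |
| Physical, normal → CS at any visit | – | – | yes |
| Physical, NCS → CS at any visit | – | – | no |

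Two rows fall outside every examination table: the third and the last.

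*Reading assumptions.* The SAP spells out the three categories for the neurological examination; for the physical examination I infer that NCS exists from the wording of the CS category. I read the Visit 9/ET table as including the early termination examination, whatever visit label SAP 4.2.1 gives it elsewhere.

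*How wide the neurological gap is.* Visits 6 and 8 have only the brief examination (Protocol 8.2.6, 8.3.3), which covers mental status, consciousness, reflexes, strength and coordination (11.7.6.2). Sensory systems, cranial nerves and speech belong to the complete examination (11.7.6.1) and are not scheduled at those visits. The gap there is therefore confined to the brief-examination items.

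*Size, for the any-visit table taken alone.* Let r be the risk of becoming CS, assumed equal from normal and from NCS.

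- New CS cases: r × (normal + NCS)
- Counted by the table: r × normal
- Share missed: NCS / (normal + NCS)

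With 50 children, none CS at Baseline, and an assumed 10%, 30% or 50% NCS on an item:

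- 10%: 5 children cannot be counted; 5/(45 + 5) = 10% missed
- 30%: 15 children; 15/(35 + 15) = 30% missed
- 50%: 25 children; 25/(25 + 25) = 50% missed

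The share is larger if NCS children are more likely to worsen than normal ones, and smaller if they are less likely.

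**The case against.** The strongest reply is that these events are tabulated elsewhere. Under Protocol 11.1.1 an adverse event includes an unfavourable sign that worsens after the initial visit, and signs of the epilepsy itself count if they increase to a clinically significant degree. A move from NCS to CS would ordinarily qualify, for neurological as well as physical findings, so the silence of 11.7.6 is not decisive. SAP 8.2.2 then tabulates treatment-emergent events separately for Titration and Maintenance and by syndrome, with no filter on Baseline examination status. This stands. What it leaves is reliance on the investigator's judgement about signs of the underlying condition, and preferred-term tables that do not show change by examination item.

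A reader might infer that neurological worsening at the end of titration goes wholly untabulated, or that the tables describe only the healthier children. The documents do not support either. Table 1 counts NCS to CS present at Visit 9/ET, including a child examined on early withdrawal while worse, and the adverse event tables are a further route.

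It can also be said that examination findings are neither primary nor secondary variables, that Protocol 13.3.3 only permits shift tables, and that the laboratory definition in SAP 8.5 also requires a normal Baseline. All true, and no commitment is broken. But laboratory parameters in hematology, chemistry and endocrinology also get changes from Baseline and post-Baseline extremes, which keep worsening visible; the examinations have no equivalent.

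**Conclusion.** The point holds as a minor tabulation gap. NCS to CS is in no physical examination table. For the neurological examination it is missed only when it appears at a visit other than Visit 9/ET and is not present at Visit 9/ET. The data are collected, listed, and should reach the adverse event tables.

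The size cannot be fixed from the documents. The 10% to 50% range rests on assumed Baseline NCS rates and equal risk, and applies to the any-visit table alone. It should not be read as the share of all new CS neurological findings that the plan would miss, because Table 1 recovers those present at Visit 9/ET.

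**What to change.** In SAP 8.6.3, for both any-visit tables:

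- change the starting group from Baseline normal to Baseline normal or abnormal, not clinically significant;
- show the counts by Baseline category, so the normal-Baseline figures stay readable on their own;
- base percentages on children not CS at Baseline who have at least one post-Baseline examination of that item.

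A physical examination shift to Visit 9/ET, matching the neurological one, is optional and not needed once the filter is widened.

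The cost is a wording change, a changed filter and one extra row per item, using data already collected. The downside is slightly higher reported rates of new clinically significant findings.

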#### 8.6.4 Tanner stage assessment

The Tanner stage is a measurement for the subject's sexual development used for subjects pubescent at Visit 1. It is a 3-item scale (for females: breasts, pubic hair, and overall stage; and for males: genitals, pubic hair, and overall stage) with 5 possible stages (I, II, III, IV, or V).

Shift tables will be produced showing the change in Tanner stage from Visit 1 to Visit 9/ET by gender for each of the 3 single items. Percentages will be based on the number of subjects with at least 1 nonmissing value at Visit 1 or Visit 9/ET.

#### 8.6.5 Achenbach Child Behavior Checklist

The Achenbach CBCL is a questionnaire intended to evaluate a child's competencies and behavioral/emotional problems. Depending on the subject's age, 1 of 2 versions of the Achenbach CBCL is used. The CBCL/1½-5 is intended for use in children 18 months to 5 years and 11 months of age at Baseline. For subjects ≥6 years to <18 years at Baseline, the CBCL/6-18 will be used. For each subject, the same version that is used at Visit 2 (Baseline) should be used at all following visits.

The CBCL/1½-5 comprises 100 questions and the CBCL/6-18 comprises 120 questions with the response options of:

- 0=not true (as far as known)
- 1=somewhat or sometimes true
- 2=very true or often true

The CBCL/1½-5 will be grouped according to syndrome scales as given in [Table 8-1](#).

**Table 8-1: CBCL/1½-5**

Syndrome scale	Questions
Aggressive behavior	8, 15, 16, 18, 20, 27, 29, 35, 40, 42, 44, 53, 58, 66, 69, 81, 85, 88, 96
Anxious/depressed	10, 33, 37, 43, 47, 68, 87, 90
Attention problems	5, 6, 56, 59, 95
Emotionally reactive	21, 46, 51, 79, 82, 83, 92, 97, 99
Sleep problems	22, 38, 48, 64, 74, 84, 94
Somatic complaints	1, 7, 12, 19, 24, 39, 45, 52, 78, 86, 93
Withdrawn	2, 4, 23, 62, 67, 70, 71, 98
Other problems	3, 9, 11, 13, 14, 17, 25, 26, 28, 30, 31, 32, 34, 36, 41, 49, 50, 54, 55, 57, 60, 61, 63, 65, 72, 73, 75, 76, 77, 80, 89, 91, 100

The CBCL/6-18 will be grouped according to empirically based syndrome scales as given in [Table 8-2](#).

**Table 8–2: CBCL/6-18**

Syndrome scale	Questions
Aggressive behavior	3, 16, 19, 20, 21, 22, 23, 37, 57, 68, 86, 87, 88, 89, 94, 95, 97, 104
Anxious/depressed	14, 29, 30, 31, 32, 33, 35, 45, 50, 52, 71, 91, 112
Attention problems	1, 4, 8, 10, 13, 17, 41, 61, 78, 80
Rule-breaking behavior	2, 26, 28, 39, 43, 63, 67, 72, 73, 81, 82, 90, 96, 99, 101, 105, 106
Social problems	11, 12, 25, 27, 34, 36, 38, 48, 62, 64, 79
Somatic complaints	47, 49, 51, 54, 56a, 56b, 56c, 56d, 56e, 56f, 56g,
Thought problems	9, 18, 40, 46, 58, 59, 60, 66, 70, 76, 83, 84, 85, 92, 100
Withdrawn/depressed	5, 42, 65, 69, 75, 102, 103, 111

Standardized T-scores are determined for each subject's raw syndrome and overall scores based on the subject's age and sex. Tables mapping each raw score to the appropriate T-score are provided in the CBCL Professional Manual and will be reproduced programmatically.

For each questionnaire (CBCL/1½-5 and CBCL/6-18, respectively), calculated T-score values and change from Baseline for each CBCL syndrome as given in Table 8–1 and Table 8–2, respectively, will be summarized by visit. The summaries will be presented by the questionnaire's age groups (18 months to 5 years and ≥6 years to <18 years) instead of the ones defined in Section 3.2.5.

#### 8.6.6 BRIEF-P and BRIEF assessment

The BRIEF-P and BRIEF are validated tools that will be used for the evaluation of subjects ≥2 to <5 years of age, and ≥5 years of age, respectively. For each subject, the same version (BRIEF-P or BRIEF) that is used at Visit 2 (Baseline) should be used at Visit 9/ET.

##### 8.6.6.1 BRIEF-P scores

The BRIEF-P form comprises 63 questions with entry options N (never: scored as 1 point), S (sometimes: scored as 2 points), and O (often: scored as 3 points).

The 63 items sum up to the raw Global Executive Composite (GEC) score which ranges from 63 to 189. Higher scores are reflecting poorer functioning.

The 3 subscale scores and 5 individual component scores that make up these subscale scores are outlined in Table 8–3.

**Table 8–3: BRIEF-P questionnaire scoring**

Scale/Index	Questions
Inhibit	3, 8, 13, 18, 23, 28, 33, 38, 43, 48, 52, 54, 56, 58, 60, 62
Shift	5, 10, 15, 20, 25, 30, 35, 40, 45, 50
Emotional Control	1, 6, 11, 16, 21, 26, 31, 36, 41, 46
Inhibitory self-control	All from {Inhibit and Emotional Control}

**Table 8–3: BRIEF-P questionnaire scoring**

Scale/Index	Questions
Flexibility	All from {Shift and Emotional Control}
Working Memory	2, 7, 12, 17, 22, 27, 32, 37, 42, 47, 51, 53, 55, 57, 59, 61, 63
Plan/Organize	4, 9, 14, 19, 24, 29, 34, 39, 44, 49
MI	All from {Working Memory and Plan/Organize}
GEC Score	1-63

MI=Metacognition Index, GEC=Global Executive Composite

Standardized T-scores are determined from each subject's raw GEC, Behavioral Regulation Index (BRI), Metacognition Index (MI), and component scores based on the subject's age and sex. Tables that map each raw score to the appropriate T-score are provided in the BRIEF-P Professional Manual and will be reproduced programmatically.

Calculated T-score values and change from Baseline for the 2 indexed scores (BRI and MI), and GEC for the BRIEF-P questionnaire will be summarized by visit for the respective age group ( $\geq 2$  to  $< 5$  years), ie, the age groups as defined in [Section 3.2.5](#) will not be used.

#### 8.6.6.2 BRIEF scores

The BRIEF form comprises 86 questions with entry options N (never: scored as 1 point), S (sometimes: scored as 2 points), and O (often: scored as 3 points).

The first 72 items sum up in the GEC score which ranges from 72 to 216, with higher scores reflecting poorer functioning.

The 2 subscale scores and 8 individual component scores that make up these subscale scores are outlined in [Table 8–4](#).

**Table 8–4: BRIEF questionnaire scoring**

Scale/Index	Questions
Inhibit	38, 41, 43, 44, 49, 54, 55, 56, 59, 65
Shift	5, 6, 8, 12, 13, 23, 30, 39
Emotional Control	1, 7, 20, 25, 26, 45, 50, 62, 64, 70
BRI	All from {Inhibit, Shift, and Emotional Control}
Initiate	3, 10, 16, 47, 48, 61, 66, 71
Working Memory	2, 9, 17, 19, 24, 27, 32, 33, 37, 57
Plan/Organize	11, 15, 18, 22, 28, 35, 36, 40, 46, 51, 53, 58
Organization of Materials	4, 29, 67, 68, 69, 72
Monitor	14, 21, 31, 34, 42, 52, 60, 63
MI	All from {Initiate, Working Memory, Plan/Organize, Organization of Materials, and Monitor}

**Table 8–4: BRIEF questionnaire scoring**

Scale/Index	Questions
GEC Score	1-72

BRI=Behavioral Regulation Index, MI=Metacognition Index, GEC=Global Executive Composite

Standardized T-scores are determined from each subject's raw GEC, BRI, MI, and component scores based on the subject's age and sex. Tables that map each raw score to the appropriate T-score are provided in the BRIEF Professional Manual and will be reproduced programmatically.

Calculated T-score values and change from Baseline for the 2 indexed scores (BRI and MI), and GEC for the BRIEF questionnaire will be summarized by visit for the respective age group ( $\geq 5$  years), ie, the age groups as defined in [Section 3.2.5](#) will not be used.

## 9 ANALYSES OF EFFICACY VARIABLES

All analyses of preliminary efficacy variables will be conducted for the FAS.

### 9.1 Preliminary Efficacy Variables

#### 9.1.1 Seizure days

Days with seizures per 28 days for each seizure type and study period will be calculated as described for the generalized seizures in [Section 8.1.2](#).

Percent change in seizure days is calculated as the respective seizure days per 28 days during the respective period (Titration Period and Maintenance Period) minus respective seizure days per 28 days during the Baseline Period divided by seizure days per 28 days during the Baseline Period and then multiplied by 100.

Descriptive statistics will be used to summarize the observed values as well as absolute and percent changes from Baseline in seizure days per 28 days by study period (Baseline, Titration, and Maintenance Period, respectively). Summaries will be provided for the following seizure types:

- Any generalized seizures (absence, myoclonic, clonic, tonic, tonic-clonic, atonic, partial evolving to secondarily generalized)
- Absence seizures
- Myoclonic seizures
- Clonic seizures
- Tonic seizures
- Tonic-clonic seizures
- Atonic seizures

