4.2 Preliminary efficacy variables

Variables used to assess preliminary efficacy will include:

- Change in days with absence seizures per 28 days from the Baseline Period to the Maintenance Period
- Change in days with myoclonic seizures per 28 days from the Baseline Period to the Maintenance Period
- Change in days with clonic seizures per 28 days from the Baseline Period to the Maintenance Period
- Change in days with tonic seizures per 28 days from the Baseline Period to the Maintenance Period
- Change in days with tonic-clonic seizures per 28 days from the Baseline Period to the Maintenance Period

- Change in days with atonic seizures per 28 days from the Baseline Period to the Maintenance Period
- Change in days with partial evolving to secondarily generalized seizures per 28 days from the Baseline Period to the Maintenance Period
- Percent change in days with any generalized seizures (absence, myoclonic, clonic, tonic, tonic-clonic, atonic, partial evolving to secondarily generalized) per 28 days from the Baseline Period to the Maintenance Period
- Percent change in days with absence seizures per 28 days from the Baseline Period to the Maintenance Period
- Percent change in days with myoclonic seizures per 28 days from the Baseline Period to the Maintenance Period
- Percent change in days with clonic seizures per 28 days from the Baseline Period to the Maintenance Period
- Percent change in days with tonic seizures per 28 days from the Baseline Period to the Maintenance Period
- Percent change in days with tonic-clonic seizures per 28 days from the Baseline Period to the Maintenance Period
- Percent change in days with atonic seizures per 28 days from the Baseline Period to the Maintenance Period
- Percent change in days with partial evolving to secondarily generalized seizures per 28 days from the Baseline Period to the Maintenance Period
- Changes in count of generalized spike-wave discharges on 24-hour ambulatory EEG from Visit 2 to Visit 9 or at Early Termination
- Changes in count of 3Hz spike-wave discharges (during waking hours) on 24-hour ambulatory EEG from Visit 2 to Visit 9 or at Early Termination
- Clinical Global Impression of Change upon completion of the Maintenance Period (Termination) or at Early Termination
- Caregiver's Global Impression of Change upon completion of the Maintenance Period (Termination) or at Early Termination

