13.6 Handling of dropouts or missing data

Subjects who prematurely discontinue the study will be evaluated based on the data collected at each visit attended.

To assess the change and percent change in seizure days for generalized seizure types (absence, myoclonic, clonic, tonic, tonic-clonic, atonic, and partial evolving to secondarily generalized) and any generalized seizures from the Baseline Period to the Maintenance Period for subjects who prematurely discontinue the study, a last observation carried forward convention will be applied in the following manner to obtain an estimate for the Maintenance Period:

- Subjects discontinued prematurely during the Titration Period: estimates will be calculated using all available data in the Titration Period and carried forward for the Maintenance Period.
- Subjects discontinued prematurely during the Maintenance Period: estimates will be calculated using all available data in the Maintenance Period and carried forward for the entire Maintenance Period.
- Subjects completing the Maintenance Period: estimates will be calculated using all data from the Maintenance Period.

The imputation for data will not be carried forward into the End-of-Study Period.

No further substitution of missing data will be conducted.

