## **2.2.2 Efficacy variables**

### **2.2.2.1 Preliminary efficacy variables**

Variables used to assess preliminary efficacy will include:

- Change in days with absence seizures per 28 days from the Baseline Period to the Maintenance Period
- Change in days with myoclonic seizures per 28 days from the Baseline Period to the Maintenance Period
- Change in days with clonic seizures per 28 days from the Baseline Period to the Maintenance Period
- Change in days with tonic seizures per 28 days from the Baseline Period to the Maintenance Period
- Change in days with tonic-clonic seizures per 28 days from the Baseline Period to the Maintenance Period
- Change in days with atonic seizures per 28 days from the Baseline Period to the Maintenance Period

- Change in days with partial evolving to secondarily generalized seizures per 28 days from the Baseline Period to the Maintenance Period
- Percent change in days with any generalized seizures (absence, myoclonic, clonic, tonic, tonic-clonic, atonic, partial evolving to secondarily generalized) per 28 days from the Baseline Period to the Maintenance Period
- Percent change in days with absence seizures per 28 days from the Baseline Period to the Maintenance Period
- Percent change in days with myoclonic seizures per 28 days from the Baseline Period to the Maintenance Period
- Percent change in days with clonic seizures per 28 days from the Baseline Period to the Maintenance Period
- Percent change in days with tonic seizures per 28 days from the Baseline Period to the Maintenance Period
- Percent change in days with tonic-clonic seizures per 28 days from the Baseline Period to the Maintenance Period
- Percent change in days with atonic seizures per 28 days from the Baseline Period to the Maintenance Period
- Percent change in days with partial evolving to secondarily generalized seizures per 28 days from the Baseline Period to the Maintenance Period
- Changes in count of generalized spike-wave discharges on 24-hour ambulatory EEG from Visit 2 to Visit 9 or at Early Termination (ET)
- Changes in count of 3Hz spike-wave discharges (during waking hours) on 24-hour ambulatory EEG from Visit 2 to Visit 9 or at ET
- Clinical Global Impression of Change upon completion of the Maintenance Period (Termination) or at ET
- Caregiver's Global Impression of Change upon completion of the Maintenance Period (Termination) or at ET

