### **3.9 Changes to protocol-defined analyses**

Not applicable.

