#### **4.2.2 Missing data**

With respect to AEs, events with missing intensity will be assumed to be severe. Events with missing relationship to LCM per the investigator will be assumed to be related.

To assess the change and percent change in seizure days for any generalized seizures from the Baseline Period to the Maintenance Period for subjects who prematurely discontinue the study, a

last observation carried forward convention will be applied in the following manner to obtain an estimate for the Maintenance Period:

- Subjects discontinued prematurely during the Titration Period: estimates will be calculated using all available data in the Titration Period and carried forward for the Maintenance Period.
- Subjects discontinued prematurely during the Maintenance Period: estimates will be calculated using all available data in the Maintenance Period and carried forward for the entire Maintenance Period.
- Subjects completing the Maintenance Period: estimates will be calculated using all data from the Maintenance Period.

Missing values for other safety or preliminary efficacy variables will be not imputed.

No imputation of missing values associated with an individual date or visit is planned, with the exception of partial date information for AEs and medications in order to determine whether they are treatment-emergent or concomitant, respectively, and for medical resources to define in which study period these were used. For details see Section 4.2.3.

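### SAP 9.1.1 plans no summary for secondarily generalized seizures, and SAP 4.2.2 conflicts with SAP 9.1.1/8.1.2 and Protocol 13.6 on carry-forward for individual seizure types

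*SAP*

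**What the plan says.** **Variables.** SAP 2.2.2.1 keeps as a preliminary efficacy variable "Change in days with partial evolving to secondarily generalized seizures per 28 days from the Baseline Period to the Maintenance Period". Protocol 4.2 has the same entry and its companion, "Percent change in days with partial evolving to secondarily generalized seizures per 28 days from the Baseline Period to the Maintenance Period", which the SAP also repeats. Protocol 13.4.1 commits to absolute and percent change for any generalized seizures and for every generalized seizure type.

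**Planned output.** After "Summaries will be provided for the following seizure types", SAP 9.1.1 has seven entries. The first is the composite, "Any generalized seizures (absence, myoclonic, clonic, tonic, tonic-clonic, atonic, partial evolving to secondarily generalized". The others are absence, myoclonic, clonic, tonic, tonic-clonic and atonic. Each is summarised by study period: Baseline, Titration and Maintenance.

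**Carry-forward.** The rule in Protocol 13.6 opens "To assess the change and percent change in seizure days for generalized seizure types (absence, myoclonic, clonic, tonic, tonic-clonic, atonic, and partial evolving" and goes on to name any generalized seizures as well. The matching paragraph in SAP 4.2.2 opens "To assess the change and percent change in seizure days for any generalized seizures from the Baseline Period to the Maintenance Period" and does not name the types. It later adds "Missing values for other safety or preliminary efficacy variables will be not imputed". SAP 9.1.1, however, calculates each type in the manner of SAP 8.1.2, and 8.1.2 says the missing Maintenance value of a Titration drop-out is imputed according to Section 4.2.

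**Declared changes.** SAP 3.9, headed "Changes to protocol-defined analyses", is answered as not applicable.

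**The concern.** Two things look wrong.

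First, a seizure type that the SAP itself defines as an outcome has no table. This type is not a side issue. Children with mixed Type I and Type II seizures are eligible (Protocol 5.1), and Protocol 2 records that lacosamide is already approved in the EU for partial-onset seizures with or without secondary generalization. A response in this type could move the any-generalized composite, whose absolute change is a primary safety variable. Without a separate row, no summary shows how much of a composite change comes from secondarily generalized seizures and how much from Type II seizures.

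Second, the SAP can be programmed in two ways for the single types, and the two give different Maintenance denominators. The choice bears on the study's purpose. Protocol 5.4 wants to find where the drug helps and where it may cause exacerbations. Leaving in Titration is also an expected event: Protocol 6.3 lists seizure worsening among the reasons for mandatory withdrawal, and Protocol 7.2 withdraws subjects who will not reach the minimum target dose.

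**Working it through.** The plan has no figure of its own to reproduce, since no formal sample size calculation was done. The check is a comparison of sections.

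**Step 1: variables against tables.**
- Defined seizure-day efficacy variables (Protocol 4.2, SAP 2.2.2.1): 7 absolute changes (one per type) + 8 percent changes (7 types and any generalized) = 15.
- Outputs under SAP 9.1.1: 7 categories × 2 (absolute and percent change) = 14.
- One of the 14, the absolute change for any generalized seizures, is a primary safety variable (SAP 2.2.1.1) and is not among the 15. So 14 − 1 = 13 of the 15 have a summary.
- 15 − 13 = 2 have none: absolute and percent change for partial seizures evolving to secondarily generalized.

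**Step 2: which carry-forward rule applies to a single type?**
- Protocol 13.6: each named type and any generalized seizures.
- SAP 4.2.2: any generalized seizures only. The type variables are preliminary efficacy variables, so the sentence barring imputation of other such variables covers them literally.
- SAP 9.1.1 to 8.1.2: types follow the method for generalized seizures, which includes the imputation step.
- SAP 8.1.2 then points back to Section 4.2, where the narrow rule stands. The references form a loop and do not settle the matter.

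**Step 3: who is affected?**
- Completers: nobody on either reading.
- Maintenance drop-outs: little or nothing. SAP 8.1.2 divides seizure days by the days with diary information in the period, so they have a Maintenance value from their own data.
- Titration drop-outs: on the 4.2.2 reading they have no Maintenance value for a single type but do have one for any generalized seizures. On the 9.1.1/8.1.2 reading they have both. On either reading they have a Titration value for each type.

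**Step 4: size.** Let p be the share of a type table's subjects who left in Titration, m_D their mean change and m_S the mean change of the others.
- With carry-forward: (1 − p) m_S + p m_D.
- Without it: m_S.
- Difference: p (m_D − m_S).

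The documents give neither p nor the means. Assuming p = 5%, 10%, 20% or 30%, and at most all 50 planned subjects in one table, 2.5, 5, 10 or 15 subjects would lack a type-specific Maintenance value if 4.2.2 governs. For each day per 28 by which the two groups' means differ, the Maintenance mean would shift by 0.05, 0.10, 0.20 or 0.30 days. These figures show the scale only; they are not estimates for this trial. Subjects have different seizure types, and percent change cannot be computed for a child with no Baseline days of the type, so p may differ from table to table.

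**The case against.** A reader might go further and infer that the SAP has withdrawn carry-forward for single types, so that children who worsen in Titration vanish from the type results, which then describe only those who tolerated the drug and look better than the total. The documents do not support this.

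- Withdrawal is only one reading. SAP 9.1.1 directs the types to a section that imputes, and SAP 9.2 again points each type to 8.1.2 before stating the imputation for any generalized seizures.
- Titration drop-outs do not vanish. SAP 9.1.1 tabulates each type by study period, and 8.1.2 derives the rate for subjects who completed or discontinued in that period. SAP 5.1 gives reasons for discontinuation by period, and SAP 8.2.2 tabulates adverse events in Titration and those leading to discontinuation.
- Type days need not add up to the total. A day with several types counts once in the composite, so comparing the types with the whole is not a sound test.

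It can also be said that SAP 3.1 promises listings of all documented and calculated data, so the missing type has output of a kind. That is right: what is missing is a summary table.

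Finally, Protocol 17.1 classes secondarily generalized seizures under partial seizures, so one might argue that they fall outside the Protocol 13.4.1 promise. This does not rescue the omission. Protocol 13.6 names them among the generalized types, and both documents list them as variables in their own right.

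These replies narrow the carry-forward half to an unresolved conflict confined to the Maintenance column. The missing row is untouched.

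**Conclusion.** The missing row is certain: 2 of 15 defined seizure-day efficacy variables have no planned summary, and nothing in the SAP records a decision to drop them.

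The carry-forward problem is a contradiction within the SAP, together with an undeclared narrowing of Protocol 13.6 in SAP 4.2.2. Exclusion of Titration drop-outs from the type-specific Maintenance columns follows only if 4.2.2 takes precedence, which the SAP does not say. Its effect on the results cannot be sized from the documents.

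All these summaries are descriptive, in an exploratory study. The primary any-generalized variable keeps its carry-forward under both SAP 4.2.2 and 8.1.2, so no primary result changes. The point should be corrected because two programmers following the SAP could report different denominators, and SAP 3.9 would tell the reader that the protocol had been followed.

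**What to change.** 1. Add partial seizures evolving to secondarily generalized as an eighth entry in the SAP 9.1.1 list. All 15 variables are then summarised.
2. In SAP 4.2.2, restore the Protocol 13.6 scope, so that the carry-forward covers each named type as well as any generalized seizures and agrees with 9.1.1 and 8.1.2.
3. If the narrower rule is intended, keep 4.2.2, say in 9.1.1 that the imputation step of 8.1.2 does not apply to single types, and record the departure with its reason in SAP 3.9.

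The cost is SAP wording and one more set of tables, with no new data. Option 2 has an interpretive price: it puts Titration data, collected while doses are being stepped up, into the Maintenance estimate. The protocol already accepts that price, and a footnote giving the number of carried-forward subjects in each Maintenance column would make it visible.
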